9.4.1.2 Statistical Analysis

We expect to eliminate approximately 2-3% of genes in through pre-processing and filtering. The data will be randomly divided into a separate training set and a test set. 20 Baseline and 20 Week 24 samples will be used for training. The remaining 10 baseline and 10 week 24 samples will be used for testing. Using criteria such as 2-fold differences in gene expression between the two measured time points within the group of patients and a false discovery rate (the percentage of genes that will be identified by chance) of less than 2%, Significance Analysis of Microarrays (SAM) [59]) will be applied to the training set to rank order genes that best can predict differences in gene expression profiles between the two time points. The SAM method identifies genes with statistically significant changes in expression by computing a score for each gene relative to the gene specific standard deviation. Genes with scores greater than a certain (adjustable) threshold will be declared significant.

The set of highest ranking genes identified with the SAM procedure will then be clustered using unsupervised hierarchical clustering analysis [60]. The purpose of this clustering analysis is to confirm the results from SAM and to further explore the microarray data in order to possibly reveal unknown subclasses. In unsupervised hierarchical clustering, no predefined reference vectors are used and the data is not partitioned into a particular cluster in a single step. Instead, a series of partitions takes place. Next, we will use methods such as prediction analysis of microarrays (PAM) based on nearest shrunken centroids [61] to devise a cross-validated gene expression predictor for these cluster-defined classes. The PAM method is a modification of the more standard nearest-centroid method. Each class centroid is shrunk toward the overall centroids after standardizing by the within-class standard deviation. The test set will then be used for validation of our

predictor. The genes that best predict the classes will be examined for similarities such as possibly participating in common genetic pathways.

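### Clustering the training arrays on SAM-selected genes is not independent confirmation of SAM, and cross-validation begun after gene selection and class definition is optimistic

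*Combined protocol and SAP*

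**What the plan says.** The relevant text is section 9.4.1.2, which serves the primary endpoint in section 9.2.1. The steps come in this order.

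1. Split: "The data will be randomly divided into a separate training set and a test set". Then "20 Baseline and 20 Week 24 samples will be used for training" and "The remaining 10 baseline and 10 week 24 samples will be used for testing". The text does not say that the split is by patient.
2. Selection: SAM "will be applied to the training set to rank order genes that best can predict differences in gene expression profiles" between the two visits. The thresholds are introduced as examples: "Using criteria such as 2-fold differences in gene expression between the two measured time points", together with an FDR below 2%. The SAM score cut-off is described as adjustable, and no list size is given.
3. Clustering: "The set of highest ranking genes identified with the SAM procedure will then be clustered". On the reason, the plan says "The purpose of this clustering analysis is to confirm the results from SAM"; it adds exploration for unknown subclasses as a second aim.
4. Prediction: PAM is then used "to devise a cross-validated gene expression predictor for these cluster-defined classes".
5. Validation: the test set is used last.

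No arrays other than the training set are named for steps 3 and 4. Nothing says that SAM or the clustering is repeated within cross-validation folds, or what happens if no gene meets the criteria.

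**The concern.** SAM keeps the genes that best separate the two visits in these particular arrays. When the same arrays are clustered on those genes, the separation that drove the selection tends to reappear whether it is signal or noise, so agreement with SAM adds no independent evidence.

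The cross-validation has the same weakness twice over. Each left-out array has already helped to choose the genes, and it has already helped to define the cluster labels that the predictor is scored on. The resulting error is biased downwards.

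This is the analysis of the primary endpoint. A reader could be offered a clean dendrogram and a low cross-validated error as corroboration of an MVC gene signature, when both are partly products of the selection step.

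**Working it through.** **Plan's own figure.** The plan gives none for clustering agreement or cross-validated error. Section 9.3 gives only power for the training set (77% in its first row). That table could not be reproduced row for row, but its calculator's noise model is not in the documents and this point does not rest on it.

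**Inputs from the documents.** About 38,000 probes, of which 2–3% are filtered (37,000 used); 30 patients with 20 for training and 10 for testing; biological SD 0.4; technical SD 0.3 or 0.4; FDR below 2%; 2-fold change.

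**Assumptions not in the documents.** List length K, linkage, amount of shrinkage, correlation between genes (none, or 10 common factors), correlation between a patient's two visits, and a split by patient.

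**Method.** Data were simulated with no MVC effect. For each gene the paired SAM score is d = mean(week 24 − baseline) / (s + s0), computed on all 20 training pairs. The top K genes by |d| were kept, the arrays were clustered and cut at two, and nearest shrunken centroids were run with 10-fold cross-validation. The comparators were SAM repeated inside each fold, and the held-out arrays.

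**Result for K = 100, average linkage, technical SD 0.3 (error = 100% − accuracy; 20 to 30 runs per row).**

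| Null setting | Clusters agree with visit (training) | CV error for visit, selection outside folds | CV error for visit, selection in fold | Held-out error for visit | CV error for cluster classes |
|---|---|---|---|---|---|
| Visits uncorrelated, independent genes | 100% | 0% | 50% | 46% | 0% |
| Half of biological variance shared by a patient's visits, independent genes | 92% | 0% | 53% | 51% | 8% |
| Half shared, correlated genes | 83% | 15% | 49% | 47% | 5% |

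Randomly chosen genes gave 50–57% agreement with visit, so the excess comes from selection.

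**Dependence on within-subject correlation.** Sharing half of the biological variance means a total correlation of 0.5 × 0.16 / (0.16 + 0.09) = 0.32. Separate runs indexed by total correlation (38,000 genes, unshrunken centroids, whole subjects left out) gave, at 0, 0.3 and 0.5:
- training clusters agreeing with visit: 100%, 87% and 50%;
- error for visit with outside selection: 0%, 0% and 0.4%;
- error for visit with in-fold selection: 46%, 52% and 47%;
- error for visit held out: 49%, 53% and 46%.

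A further set of runs gave about 0% with outside selection, 44–49% in fold and 48–53% held out. For the planned cluster classes the null error was 0%, 9%, 20% and 12% at total correlations 0, 0.3, 0.5 and 0.7, and up to 23% in other runs.

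**Dependence on list length.** With the top 500 independent genes (half of biological variance shared), training clusters agree with visit only 50–53% of the time, and the cluster-class error is 18–32%. With correlated genes, agreement stays at 78–84% from 50 to 500 genes.

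**Effect of the plan's criteria.** With FDR below 2% enforced, 0 null genes passed in 40 of 40 runs. The 2-fold rule alone is also strict. In the most permissive case (technical SD 0.4, natural-log scale, uncorrelated visits) the standard error of the mean difference is sqrt(2 × 0.32 / 20) = 0.179. Then z = 0.693 / 0.179 = 3.87, the two-sided p is about 0.000107, and 37,000 × 0.000107 ≈ 4 genes. With correlation 0.5 on the same scale, z = 5.48 and 0.0016 genes are expected.

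**Is in-fold SAM enough?** No. With labels still defined by clustering all training arrays, repeating SAM in each fold moved the null cluster-class error only from 20% to 23% (correlation 0.5) and from 12% to 18% (correlation 0.7), still far below chance error.

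**The case against.** The strongest reply is that the plan puts a gate before the clustering. A reader might infer that the clustering and the cross-validation would both look convincing even if MVC did nothing. The documents do not support that as a general statement. The plan names FDR below 2% and a 2-fold change, and under the null either criterion, if enforced, leaves essentially nothing to cluster. Agreement also falls to about 50% when a patient's visits correlate at 0.5, or with long lists of independent genes; in those cases the clustering would fail to confirm SAM. What remains is that the criteria are given as examples, the cut-off is adjustable and no list length is fixed, so selection by rank is permitted. Even behind a firm gate, the same arrays cannot corroborate their own selection.

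A reader might also infer that the signature has no independent check. That is not so. The plan reserves the word validation for the 10+10 test set, which takes no part in selection, clustering or cross-validation. The safeguard is incomplete only because the predicted classes are clusters, so test arrays carry no independent label unless scored against visit, and because the split is not stated to be by patient.

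Two further points are fair. Restriction of PAM to the SAM genes is implied by the sequence, not stated; on all genes the null accuracy for cluster classes was 50–68%. And section 9.1 calls this a pilot, and exploration is a declared aim of the clustering. Neither justifies the claim of confirmation.

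**Conclusion.** The point holds in a limited form. Clustering the training arrays on genes selected to separate the visits in those arrays is not independent confirmation of SAM. Cross-validation that starts after gene selection and class definition understates the error.

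The size depends on how the list is formed. With genes taken by rank or with a relaxed threshold, no MVC effect and the top 100 genes, the error for visit is about 0–15% with outside selection, against about 44–53% done properly. For the planned cluster classes it is about 0–23%, depending mainly on within-subject correlation. Clustering agreement with visit runs from 100% down to about 50%. With FDR below 2% strictly applied, almost no null genes get this far.

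These figures rest on assumed correlation structures, list lengths, linkage and shrinkage. No run included a true effect, so the optimism when MVC does change expression is not quantified. The matter should be corrected because it governs what the primary analysis may claim; the separate test set keeps it from being fatal.

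**What to change.** Change section 9.4.1.2 as follows.

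- Describe clustering of the training arrays as display or exploration, not confirmation.
- Treat the FDR and 2-fold criteria as fixed, and state that no clustering or predictor follows if no gene passes.
- Repeat both SAM selection and class definition inside every fold, leaving out whole subjects. Alternatively, use visit as the label and repeat SAM in each fold. Repeating SAM alone is not enough while the labels come from all training arrays.
- Name held-out accuracy for baseline versus week 24, in test subjects with no array in training, as the only validation result.

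The cost is some wording and a little more code, with no new samples or patients. The reported cross-validated error will be less favourable.

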2.0 INTRODUCTION

2.1 Background (Main study)

Suboptimal CD4+ T-cell recovery during potent antiretroviral therapy (ART) is a common clinical dilemma with an incidence as high as 40% [1-4]. Reconstitution of CD4+ T-cells during viral suppression follows a biphasic pattern [5]. In the first three months of ART, CD4+ T-cells typically increase by 50 to 120 cells/mm³ [6-8] - primarily as a result of redistribution of T-cells into peripheral circulation [9, 10]. The magnitude of this early recovery is likely a function of prior T-cell destruction as lower CD4+ T-cell nadirs have been associated with limited immune recovery during therapy [2, 11]. This initial burst is followed by a second, slower, phase of T-cell repopulation (average rate of 2 to 10 cell/mm³ increase per month [6-8, 12]) which may continue for as long as 6 years [13]. This second phase is often termed the 'regenerative phase' as de novo T-cells are produced from the thymus and by peripheral expansion. However, in some individuals, the phase 2 CD4+ T-cell recovery plateaus and these patients fail to recover 'normal range' T-cells despite optimal viral suppression [3, 13].

We propose to evaluate the potential beneficial immunomodulatory-effects of MVC on CD4+ T-cell recovery during optimal viral suppression. Individuals with well-controlled HIV-infection on ART will undergo therapy intensification with MVC for 6 months followed by a 3 month post-intensification visit. The goals of this study include:

1. To determine the impact of MVC treatment intensification on host genomic responses. Whole genome (~38,000 genes) analysis on purified CD4+/CD8+ lymphocytes will be used to evaluate changes in gene expression patterns, in particular genes associated with proliferation, trafficking and activation, before and during MVC treatment intensification.
2. To evaluate differences in the rate of phase 2 CD4+ T-cell recovery before and during 6 months of MVC treatment intensification.
3. To characterize changes in immune T-cell subsets (activation, maturation and apoptosis) before and during MVC treatment intensification.
4. To develop a gene classifier of MVC treatment-responsive genes and propose a model of the impact of CCR5-inhibition on immune reconstitution during suppressive ART.

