9.2 Endpoints

9.2.1 Primary

1. Differences in gene expression profiles obtained at baseline and weeks 4 and 24.

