9.4.3.1. Analysis of Secondary Objectives

Secondary analyses will include descriptive statistics and tests of significance between pre- and post-MVC intensification. All significance tests will be two-sided and no adjustment for multiple comparisons will be made. If necessary due to assumption failures, appropriate non-parametric statistical tests will be applied.

1. Differences in the change in CD4+ T-cell absolute count and percentage from baseline to week 4 and baseline to week 24 will be compared descriptively via separate paired Student t-tests. Repeated CD4+ T-cell absolute count measured at different time points (3 historic time-points, baseline, week 4, and week 24) will be treated as the outcome variable in a linear mixed-effects model. The primary fixed effects will include time, period (MVC vs. pre-MVC), and interaction between time and period; random effects will include both intercept and slope allowing each subject to have individual starting CD4+ T-cell counts and rate of change. Baseline covariate adjustment will be included if necessary. A significant interaction term between time and period with positive coefficient will indicate if the rate of CD4 recovery is greater during MVC compared to pre-MVC.

2. Differences in the rate of CD4+ T-cell recovery (absolute count and percentage) during MVC intensification in subjects receiving a PI/r- vs. NNRTI-based regimen will be compared via the linear mixed effects model. The fixed effects will include time, regimen (PI/r vs NNRTI), and regimen-by-time interaction; random effects will include both intercept and slope. The regimen-by-time interaction term in the model will indicate the difference in CD4+ T cell recovery rates between the two regimen groups. Baseline covariate adjustment will be included if necessary.

3. Differences in gene expression profiles between subjects receiving a PI/r vs. NNRTI-based regimen at baseline and weeks 4 and 24 will be examined by comparing the gene lists generated in the primary analysis by regimen type. If necessary, statistical modeling will include a dichotomous variable to indicate regimen type.

4. Differences in the proportion of CD4+/CD8+ T-cell immune activation, maturation, regulatory and apoptosis markers between baseline and weeks 4 and 24 will be compared cross-sectionally via McNemar's test or paired t-tests as appropriate.

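### The gene predictor is trained on clusters, not on baseline versus week 24, with no cut rule or reference class, so its test-set accuracy need not describe the pre/post change

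*Combined protocol and SAP*

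**What the plan says.** Section 9.4.1.2 sets out four steps for the primary analysis.

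1. SAM ranks genes by baseline versus week 24 in the training set, with a 2-fold criterion and a false discovery rate below 2%.
2. The top-ranked genes go into unsupervised hierarchical clustering. "The purpose of this clustering analysis is to confirm the results from SAM", and also to look for subclasses not yet known. On how the tree is cut, the text says only: "Instead, a series of partitions takes place".
3. Methods such as PAM are used "to devise a cross-validated gene expression predictor for these cluster-defined classes".
4. "The test set will then be used for validation of our" predictor.

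The split is stated in samples. Twenty baseline and twenty week 24 samples are for training. "The remaining 10 baseline and 10 week 24 samples will be used for testing".

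Three other places bear on this. The primary endpoint in section 9.2.1 is "Differences in gene expression profiles obtained at baseline and weeks 4 and 24". Goal 4 in section 2.1 begins "To develop a gene classifier of MVC treatment-responsive genes". Item 3 of section 9.4.3.1 looks at PI/r versus NNRTI regimens by "comparing the gene lists generated in the primary analysis by regimen type", and allows a regimen indicator in the modelling where needed.

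**The concern.** The time-point labels are used once, at the SAM step. The predictor's target is whatever groups the clustering returns, and nothing in the plan equates those groups with baseline and week 24. Cross-validated accuracy then shows how well the clusters can be told apart, which is a different question from how well expression separates the two time points.

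The test set is the plan's only check on unseen samples, and it is the route to the classifier named in section 2.1. A test-set error needs a true class for each test sample, and the plan gives none. At least three readings fit the text: the sample's time point, a clustering of the 20 test samples alone, or a clustering of all 60 samples. If the cut and the reference class are chosen after the arrays are analysed, the result can pick the method.

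Two related gaps are smaller. Genes chosen because they differ by time point will tend to show that difference when clustered, so the clustering is not independent confirmation of SAM. And the text does not say that a patient's two samples stay on the same side of the split, although the balanced counts are consistent with that.

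**Working it through.** **The plan's own figures.** The plan states no accuracy for the predictor, so there is none to reproduce. The split adds up: 20 + 10 = 30 samples per time point, and 2 × 30 = 60, as in section 9.4.1. The power table in section 9.3 could not be reproduced. It comes from an online calculator whose noise model is not in the documents. It is not called wrong, and nothing here depends on it.

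**Inputs from section 9.3.** 38,000 genes, 500 hits, 2-fold change, biological SD 0.4, technical SD 0.3. Combined SD = √(0.4² + 0.3²) = √0.25 = 0.5.

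**Assumptions not in the documents.** Natural-log scale; half the variance shared within patient; paired t with Benjamini-Hochberg below 2% plus an observed 2-fold difference as a stand-in for SAM; samples clustered by Ward or by average-linkage correlation; two, three or four clusters; any patient subgroup split equally, 15 and 15, with a constant offset in the responding genes. Nearest shrunken centroids were used without a subgroup and plain nearest centroids with one. There were 40 runs per setting, and smaller repeat simulations (plain centroids in at least one) are included in the ranges.

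**Error of one and the same predictor on the test set, by reference class**

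| Setting | Time point | Clusters of all 60 | Clusters of test samples |
|---|---|---|---|
| No subgroup, 2 clusters | 0% | 0% | 0% |
| No subgroup, 3 clusters | 0% | 5-17% | 8-18% |
| No subgroup, 4 clusters | 0% | 10-37% | 16-36% |

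With two clusters and a subgroup offset of 2.4-fold in all responding genes, or 3.5-fold in half of them, the error is 50% against time point and about 0-3% against clusters. With the 3.5-fold offset in half the genes but four clusters, the clusters agree with time point in 100% of samples. The unstated cut alone moves the result from chance to perfect.

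**Why a subgroup can take over.** With two equal groups, time point contributes in proportion to (ln 2)² = 0.693² = 0.480 per gene. A subgroup offset F in a share s of the genes contributes s × (ln F)².

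- 2.4-fold in all genes: 1 × 0.875² = 0.766.
- 3.5-fold in half: 0.5 × 1.253² = 0.785.

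Both exceed 0.480, so a two-way cut follows the subgroup.

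This comparison does not give a general threshold. With all genes affected and 4 of 20 training patients in the subgroup, clusters still agreed with time point in 89-90% of samples at 2.1-fold, against 50% with 10 of 20. With 6 of 20, agreement was already 59-83% at 1.9-fold. Even with the 15/15 split, simulations at 1.9-fold ranged from no time-point error to 18-21%.

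**The alternative.** PAM trained on the time points had 0% held-out error with 500 or 100 hits, and 2.5% with 20 hits and no subgroup. A centroid classifier trained on time point also had 0% error in the strong-subgroup setting.

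**Precision with the patient as unit.** For 0 of 10 wrong, the exact 95% upper limit is 1 − 0.025^(1/10) = 0.308, so the interval is 0-31%. For 1 of 10 it is 0.3-45%.

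**The case against.** The strongest reply is that the primary endpoint does not need the predictor. SAM compares baseline with week 24 directly, section 9.1 calls this a pilot study, and no objective or endpoint names a predictor or an accuracy. This stands. A reader might infer that the primary analysis is circular or the gene list unsafe. The documents do not support that: SAM uses the known labels in the training set under its own error control.

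A second reply is that the two-step design is deliberate: find subclasses, then predict them. Section 2.3 also speaks of sorting responsive genes into functional groups, so the classifier in section 2.1 need not mean a time-point classifier. Subclass discovery is legitimate and the fix keeps it. But a subclass predictor still needs a cut rule and a reference class before it can be validated, and the plan has neither.

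A third reply is that SAM-selected genes will usually cluster by time, and that the large errors need either extra clusters or a strong patient offset in the same genes, for which the documents give no figure. This is correct and makes the size conditional. The plan does, however, look for subclasses and expects regimen differences. Item 3 of section 9.4.3.1 allows a regimen variable, but neither that nor the gene-list comparison checks the clusters or the predictor against regimen.

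Finally, the text literally says that the gene set is clustered. The references to classes and subclasses imply that samples are grouped, and this point reads it so. The plan also does not claim that the clustering is independent confirmation of SAM, so that remark is only a caution.

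**Conclusion.** The gap is real and limited to the predictor and its validation. As written, the test-set accuracy has no defined meaning and need not describe the pre/post change. The SAM list and the power table are unaffected.

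The size is conditional on 500 hits, a 2-fold change, an SD of 0.5 and the clustering choices listed. There is no harm with two clusters and no subgroup. With three or four clusters and no subgroup, the spread is 0% against roughly 8-35% on test-sample clusters. With two clusters and a strong, equally split subgroup, the predictor is at chance for time point while about 0-3% wrong against clusters.

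A reader might take the two subgroup examples as a fold threshold, or conclude that the predictor will fail. Neither follows: the crossover moves with subgroup size and the share of genes affected, and the documents give neither. This should be fixed before the arrays are analysed.

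**What to change.** In section 9.4.1.2:

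- Split by patient: 20 for training and 10 for testing, each patient's two samples together.
- Train PAM on baseline versus week 24 in the training set. In any cross-validation, keep a patient's two samples in the same fold.
- Lock the predictor and score it once on the 10 held-out patients against actual time point. Report an exact interval with the patient as unit, and say when a patient counts as wrong. Describe the result as pre/post change, because the study is single-arm.
- Keep the clustering, and any predictor of clusters, as exploratory. State that samples are clustered, give the cut rule and the reference class, and tabulate the clusters against time point and against PI/r versus NNRTI.
- Do not present clustering of SAM-selected genes as independent confirmation of SAM.

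The cost is SAP wording and a little computing, with no new samples or visits. The cluster predictor becomes exploratory, and the held-out estimate is imprecise: a perfect score on 10 patients still leaves an interval of 0-31%. A smaller change, stating only the cut rule, reference class and accuracy measure, would make the validation interpretable but would still not make it a measure of pre/post change unless time point is the class.
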